### **4 CONCOMITANT MEDICATIONS/MEASURES**

Concomitant medications will be recorded well.

### **5 BIOSPECIMEN COLLECTION**

#### **5.1 SAMPLE STORAGE, TRACKING AND DISPOSITION**

All of the biospecimens are considered biohazard, and should be managed according to Taiwan CDC's guidelines. Store serum will be shipped to contract laboratory, and will be destroyed if no more extended studies permitted.

### **6 DATA COLLECTION AND EVALUATION**

#### **6.1 DATA COLLECTION**

The study will use eCRF/EDC for data collection. Safety laboratory data will be entered into eCRF by authorized personnel at Investigational sites. Real-time RT-PCR data will be managed and stored within the laboratory information management system and only the date and time of specimens are recorded in the eCRF. Safety laboratory data will be integrated with the consolidated clinical data before database lock.

All records should be kept in conformance to applicable national laws and regulations.

Adverse events will be recorded according to the Division of AIDS (DAIDS) Table for Grading the Severity of Adult and Pediatric Adverse Events(Appendix 3), and will be coded using the current MedDRA thesaurus (Version 19.0); concomitant medication will be coded using World Health Organization Collaborating Centre for Drug Statistics Methodology Anatomical Therapeutic Chemical/defined daily dose (WHOC ATC/DDD).

#### **6.2 CRITERIA OF PRIMARY ENDPOINTS**

##### **6.2.1 Primary efficacy endpoints**

- Transition time of SARS-CoV-2 nucleic acid rRT-PCR from positive results to negative results in respiratory tract specimen on day 0, 2, 4, 6, 8, 10, 12, 14. For evaluation of primary efficacy endpoint, the type of respiratory tract specimens in each assessment day should be the same with Day 0.

### **6.3 SECONDARY ENDPOINTS**

#### **6.3.1 Evaluation of Efficacy**

- Virological clearance rate at day 8
- AUC of viral load on day 0, 2, 4, 6, 8, 10, 12, 14

For the above 2 secondary efficacy evaluations, the type of respiratory tract specimens in each assessment day should be the same with Day 0.

- Time to Clinical recovery (TTCR):

TTCR is defined as the time (in hours) from randomization (active or placebo) until normalization of fever, respiratory rate, and oxygen saturation, and alleviation of cough, sustained for at least 72 hours.

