## **3 STUDY IMPLEMENTATION**

### **3.1 STUDY DESIGN**

This is a multi-center, randomized, open-label, controlled trial to evaluate the efficacy and tolerability of Hydroxychloroquine Sulfate (HCQ) in adult Patients with mild to moderate coronavirus disease (COVID-19) compared to standard of care treatment (SOC). The primary endpoint for the study is to evaluate the efficacy of HCQ, with respect to the time to negatively rRT-PCR assessments from the randomization date up to 14 days. The secondary endpoint is to evaluate the efficacy of HCQ in the aspect of virological assessments and the change of clinical symptoms. In addition, the safety and tolerability of HCQ will be evaluated during treatment period in COVID-19 patients.

The study will employ an open-label parallel design, to evaluate the efficacy and safety between hydroxychloroquine sulfate (plaquenil) and controlled standard of care treatment. The administration plan of HCQ is 400 mg bid on Day 1 and 200 mg bid for 6 days on Day 2-7. All of the enrolled subjects will receive standard of care. The comparison group will receive standard of care, i.e., supportive treatment for subjects with mild COVID-19 clinical illness, and antimicrobial therapy for subjects who developed moderate COVID-19 clinical illness (ceftriaxone 2gm daily for 7 days ± azithromycin 500mg on Day1 and 250mg on Day2-5; or levofloxacin 750 mg daily for 5 days, or levofloxacin 500mg daily or moxifloxacin 400mg daily for 7-14 days for the subjects who had allergic history to ceftriaxone or azithromycin, or per physician's discernation). Oseltamivir 75 mg bid for 5 days will be given for subjects who have concomitant influenza A or B infection. The subjects will be randomly assigned to a 2:1 ratio to receive HCQ + SOC, or SOC alone. The estimated case number will be 30:15. No dose reduction, modification, or change in the frequency of HCQ will be recommended during the study period.

The investigators may determine to switch to HCQ treatment arm on Day 8 if the subjects developed progression of pneumonia clinically, or roentegenographically, or had persistent high viral load without 10 log of decline, compared to baseline data.

An independent data monitoring committee (IDMC) will be instituted to ensure external objective

medical and/or statistical review of efficacy to protect the ethical interests and well-being of participants and to protect the scientific validity of the study.

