#### Normalization and alleviation criteria:

- Fever -  $\leq 36.9^{\circ}\text{C}$  or -axilla,  $\leq 37.2^{\circ}\text{C}$  oral,
- Respiratory rate -  $\leq 20/\text{minute}$  on room air,
- Oxygen saturation -  $\geq 94\%$  on room air,
- Cough - mild or absent on a patient reported scale of severe, moderate, mild, absent
- Frequency of CNS symptoms (e.g. headache, dizziness, impaired consciousness, ataxia, acute cerebrovascular disease, and epilepsy)
- Frequency of respiratory progression:

Defined as  $\text{SpO}_2 < 94\%$  on room air or  $\text{PaO}_2/\text{FiO}_2 < 300$  mmHg and requirement for supplemental oxygen or more advanced ventilator support

- Proportion of Participants Discharged by Day 14
- The mortality rate of subjects at week 2 and week 3

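### TTCR sets a support-free condition for respiratory rate and saturation but none for fever or cough, so in this open-label trial symptomatic treatment can be scored as recovery

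*Protocol*

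**What the plan says.** Section 6.3.1 runs TTCR from randomization "until normalization of fever, respiratory rate, and oxygen saturation, and alleviation of cough, sustained for at least 72 hours". The list headed "Normalization and alleviation criteria" then sets the component rules:

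- Fever: at most 36.9 °C axillary or 37.2 °C oral.
- Respiratory rate: at most 20 per minute, on room air.
- Oxygen saturation: at least 94%, on room air.
- Cough: "mild or absent on a patient reported scale of severe, moderate, mild, absent".

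Section 3.1 states the design, "The study will employ an open-label parallel design", and the background care, "All of the enrolled subjects will receive standard of care". That care is described as "supportive treatment for subjects with mild COVID-19 clinical illness", with named antimicrobials for moderate illness. The content of supportive treatment is not listed.

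The whole of section 4 is "Concomitant medications will be recorded well". Section 6.1 adds that these medications will be coded to the WHO ATC/DDD system. Neither section mentions start and stop times or links medication use to TTCR.

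**The concern.** The room-air condition shows that, for two of the four components, the authors did not want recovery to be credited while it depended on support. The other two components have no such protection. A subject on regular antipyretics whose temperature stays under the cut-off for 72 hours meets the fever item, even if the fever might return without the drug. A cough kept mild by an antitussive meets the cough item in the same way.

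Under blinding, such use would tend to balance between arms. Here the staff who give symptomatic treatment know who is receiving HCQ, and so do the subjects who grade their own cough. A TTCR difference between arms could then reflect different use of symptomatic drugs, or different self-report, rather than an effect of HCQ. Without timed medication data, the report could not tell these apart.

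**Working it through.** The protocol gives no figure to reproduce here, so the check sets its provisions side by side and then asks what would be needed to size an effect.

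**1. Condition on each component (section 6.3.1)**

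| Component | Criterion | Must be free of support? |
|---|---|---|
| Respiratory rate | ≤ 20/min | Yes, room air |
| Oxygen saturation | ≥ 94% | Yes, room air |
| Fever | ≤ 36.9 °C axillary or ≤ 37.2 °C oral | No condition |
| Cough | Mild or absent, self-rated | No condition |

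**2. Is the gap closed elsewhere?** No. Section 3.1 neither restricts nor standardises symptomatic treatment. Section 4 only records it. The coding in section 6.1 would identify the drug class but not when a drug was taken relative to a temperature reading or cough rating.

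**3. Does the 72-hour rule close it?** Only in part. It removes a short dip after a single dose. It does not remove suppression by regular dosing, which can last 72 hours.

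**4. Which components are likely to decide TTCR?** Section 2.1.1 admits subjects with fever or acute upper respiratory symptoms whose disease is mild, or is pneumonia that needs no supplemental oxygen. Many will probably meet the saturation criterion at entry, and perhaps the respiratory-rate criterion too. Fever and cough, the two unprotected items, may then often fix the recovery time. This is an inference from the entry criteria, not a statement in the protocol.

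**5. Can the effect be sized?** As a simplification, let F be the time from which temperature stays normal without treatment, F′ ≤ F the same time under an antipyretic, and M the latest of the other three component times. All four items must hold together, so TTCR follows the latest of them:

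- TTCR without suppression depends on max(F, M).
- TTCR with suppression depends on max(F′, M).
- Advance = max(F, M) − max(F′, M).

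If F ≤ M, the advance is 0, because fever was not the last item to resolve. If F > M, the advance is F − max(F′, M), which never exceeds F − F′. A subject who enters on respiratory symptoms and never has a fever gains nothing through the fever item. The same reasoning applies to cough.

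The bias in a comparison of means is the difference between arms in the average advance. It needs use by arm, F − F′, and how often each item resolves last. The protocol gives none of these, so no figure in hours can be derived.

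**6. Direction.** Heavier use in the SOC-alone arm would shorten its TTCR and hide a benefit of HCQ. Heavier use in the HCQ arm would create an apparent benefit. The protocol does not say which to expect.

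**7. Would a medication-free rule alone remove the problem?** No. If a dose within the look-back disqualifies the reading, each dose delays scored recovery. The more heavily medicated arm, advanced under the current rule, would be delayed under the new one. A dose taken for headache or muscle pain, both among the mild-illness symptoms in section 2.1.1, would also hold back an afebrile subject. The two scorings err in opposite directions, which is why they are informative together and why neither is enough alone.

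**The case against.** The strongest reply is that recovery under usual care, whatever symptomatic treatment is given, is a legitimate target when both arms receive standard of care. A room-air rule on two items does not make the lack of a parallel rule on the others a contradiction. That stands, and it is a reason to keep the current definition. It does not answer the open-label problem: if use differs by arm, the usual-care result mixes the effect of HCQ with that of the symptomatic drugs, and the reader needs to see whether it does.

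A second reply is that antipyretics and antitussives are not named anywhere, and that supportive treatment is not itemised and is tied to mild illness. This is correct. Their use is a reasonable inference for patients with fever and cough, not a documented fact. The gap in the definition exists whatever the rate of use.

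A third reply is that scoring rules and sensitivity analyses can be left to an SAP, which is not at hand. This is partly right. But the component conditions are fixed in the protocol, for two of four items, and an SAP cannot use medication times that were never collected.

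A reader might go further and infer that TTCR is the main clinical endpoint. The protocol does not rank it above respiratory progression, discharge by Day 14, CNS symptoms or mortality, and section 1.2.2 describes the symptom objective as exploratory. The PCR-based primary endpoint in section 6.2.1 is defined without reference to temperature or cough.

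**Conclusion.** The point holds for one of several secondary clinical endpoints. As written, a fever or cough suppressed for 72 hours counts as recovery, and the cough item rests on self-report by subjects who know their arm. The definition itself is plain from the text. That it matters in practice rests on two assumptions: that antipyretics or antitussives will be used, and that their use or the cough reporting may differ between arms.

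It would be tempting to conclude that TTCR is biased in a known direction, or by a stated number of hours. The documents support neither, because use by arm, the time gained and the last item to resolve are all unknown. Nor do they support replacing the definition with a medication-free one, which would move the bias rather than remove it. The case is for collecting the data and scoring TTCR in more than one way, which shows whether a difference depends on symptomatic treatment or unblinded self-report.

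**What to change.** In section 6.3.1, keep the current TTCR and prespecify two further versions beside it:

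- (a) TTCR in which fever counts as resolved only when no antipyretic, and cough only when no antitussive, was taken within a fixed look-back (for example 24 h), throughout the 72 hours.
- (b) TTCR without the patient-reported cough item.

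In section 4, require the name, start time and stop time of these drugs on the concomitant-medication page. Report their use by arm with the TTCR results, and state in advance that a conclusion on TTCR will be drawn only if the versions agree.

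The cost is a few eCRF fields and two extra analyses. Version (a) can delay scored recovery in the more heavily medicated arm, or when a drug was taken for another symptom, so it should accompany the current definition and not replace it. The change affects only what is recorded and scored, not what may be given.

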#### Normalization and alleviation criteria:

- Fever -  $\leq 36.9^{\circ}\text{C}$  or -axilla,  $\leq 37.2^{\circ}\text{C}$  oral,
- Respiratory rate -  $\leq 20/\text{minute}$  on room air,
- Oxygen saturation -  $\geq 94\%$  on room air,
- Cough - mild or absent on a patient reported scale of severe, moderate, mild, absent
- Frequency of CNS symptoms (e.g. headache, dizziness, impaired consciousness, ataxia, acute cerebrovascular disease, and epilepsy)
- Frequency of respiratory progression:

Defined as  $\text{SpO}_2 < 94\%$  on room air or  $\text{PaO}_2/\text{FiO}_2 < 300$  mmHg and requirement for supplemental oxygen or more advanced ventilator support

- Proportion of Participants Discharged by Day 14
- The mortality rate of subjects at week 2 and week 3

#### **6.3.2 Evaluation of Safety**

- Frequency of serious adverse events

### **6.4 TOXICITY CRITERIA**

## **7 SAFETY REPORTING REQUIREMENTS/DATA AND SAFETY MONITORING PLAN**

### **7.1 DEFINITIONS**

#### **7.1.1 Adverse Event**

An adverse event is defined as any reaction, side effect, or untoward event that occurs during the course of the clinical trial associated with the use of a drug in humans, whether or not the event is considered related to the treatment or clinically

significant.

#### 7.1.2 Suspected adverse Event

Suspected adverse reaction means any adverse event for which there is a reasonable possibility that the drug caused the adverse event. For the purposes of IND safety reporting, 'reasonable possibility' means there is evidence to suggest a causal relationship between the drug and the adverse event. A suspected adverse reaction implies a lesser degree of certainty about causality than adverse reaction, which means any adverse event caused by a drug.

#### 7.1.3 Unexpected adverse reaction

An adverse event or suspected adverse reaction is considered "unexpected" if it is not listed in the investigator brochure or is not listed at the specificity or severity that has been observed; or, if an investigator brochure is not required or available, is not consistent with the risk information described in the general investigational plan or elsewhere in the current application. "Unexpected", also refers to adverse events or suspected adverse reactions that are mentioned in the investigator brochure as occurring with a class of drugs or as anticipated from the pharmacological properties of the drug, but are not specifically mentioned as occurring with the particular drug under investigation.

#### 7.1.4 Serious

An adverse event or suspected adverse reaction is considered serious if in the view of the investigator or the sponsor, it results in any of the following:

- Death,
- A life-threatening adverse drug experience
- Inpatient hospitalization or prolongation of existing hospitalization
- Persistent or significant incapacity or substantial disruption of the ability to conduct normal life functions
- A congenital anomaly/birth defect.
- Important medical events that may not result in death, be life-threatening, or require hospitalization may be considered a serious adverse drug experience when, based upon appropriate medical judgment, they may jeopardize the patient or subject and may require medical or surgical intervention to prevent one of the outcomes listed in this definition.

#### 7.1.5 Disability

A substantial disruption of a person's ability to conduct normal life functions.

#### 7.1.6 Life-threatening adverse drug experience

Any adverse event or suspected adverse reaction that places the patient or subject, in the view of the investigator or sponsor, at immediate risk of death from the reaction as it occurred, i.e., it does not include a reaction that had it occurred in a more severe form, might have caused death.

#### 7.1.7 Unanticipated Problem

Any incident, experience, or outcome that:

- Is unexpected in terms of nature, severity, or frequency in relation to
- (a) the research risks that are described in the IRB-approved research protocol and informed consent document; Investigator's Brochure or other study documents, and
- (b) the characteristics of the subject population being studied; **AND**
- Is related or possibly related to participation in the research; **AND**
- Places subjects or others at a *greater risk of harm* (including physical, psychological, economic, or social harm) than was previously known or recognized.

## 7.2 REC OR IRB REPORTING

Unexpected AE, SAE will be reported. And interim analysis will be reported to IRB when 22 participants are enrolled.

### 7.3 DATA AND SAFETY MONITORING PLAN

DSMB will monitor the safety of the study, and the committee will be held every 2-4 weeks after 1st participant enrolled.

#### 7.3.1 Principal Investigator/Research Team

*All protocols should include a DSM plan which describes how the investigator plans to oversee research subject safety and ensure data integrity. The PI and his/her research staff are part of the monitoring plan but may not be the only ones conducting monitoring activities for any given protocol.*

The clinical research team will meet on a regular basis *{insert frequency}* when patients are being actively treated on the trial to discuss each patient. Decisions about dose level enrollment and dose escalation if applicable will be made based on the toxicity data from prior patients.

All data will be collected in a timely manner and reviewed by the principal investigator or a lead associate investigator. Adverse events will be reported as required above. Any safety concerns, new information that might affect either the ethical and or scientific conduct of the trial, or protocol deviations and violations will

be immediately reported to the IRB using iRIS and if applicable to the Sponsor. The principal investigator will review adverse event and response data on each patient to ensure safety and data accuracy. The principal investigator will personally conduct or supervise the investigation and provide appropriate delegation of responsibilities to other members of the research staff.

### 7.3.2 Data Safety Monitoring Board (DSMB)

*A DSMB is an impartial group established to oversee a clinical trial and review the results to determine if they are acceptable. Members of a DSMB must be multidisciplinary and include members with relevant clinical and statistical expertise. The DSMB should meet at least annually or more often depending on the activity and nature of the clinical trial being monitored.*

This protocol requires monitoring by the Data Safety Monitoring Board (DSMB) as described above in Section 7.3. Interim outcome results will not be revealed to the investigators of the trial; results will be presented to the investigators prior to final accrual to the trial only if the DSMB recommends early termination of the trial.

(NOTE: the study statistician is responsible for providing the description of how the monitoring will take place, including endpoints to be monitored and the frequency or timing of monitoring.)

